2.8.2 Deaths

All deaths (on-treatment and post-treatment) will be listed, post treatment deaths will be flagged.

2.8.3 Laboratory data

Laboratory data summaries will include all assessments available for the lab parameter collected no later than 30 days or safety follow-up whichever is later after the last study treatment administration date using data from all sources. All laboratory assessments will be listed and those collected later than 30 days after the last study treatment date will be flagged in the listings.

Grading of laboratory values will be assigned programmatically as per NCI Common Terminology Criteria for Adverse Events (CTCAE) version 4.03. The calculation of CTCAE grades will be based on the observed laboratory values only, clinical assessments will not be taken into account.

CTCAE Grade 0 will be assigned for all non-missing values not graded as 1 or higher. Grade 5 will not be used. For laboratory tests that are graded for both low and high values, summaries will be done separately and labeled by direction, e.g., sodium will be summarized as hyponatremia and hypernatremia.

For laboratory tests where grades are not defined by CTCAE, results will be categorized as low/normal/high based on laboratory normal ranges.

The following summaries will be generated separately for hematology, biochemistry and urinary tests:

For laboratory tests where grades are defined by CTCAE

- Worst post-baseline CTCAE grade (regardless of the baseline status). Each patient will be counted only once for the worst grade observed post-baseline.
- Shift tables using CTCAE grades to compare baseline to the worst and from baseline to the last post-baseline on-treatment value

For laboratory tests where grades are not defined by CTCAE ,

- Shift tables using the low/normal/high/ (low and high) classification to compare baseline to the worst and from baseline to the last post-baseline on-treatment value

In addition, the following laboratory results will be summarized.

- Patients meeting categorical liver function test criteria, including Hy's Law criteria for liver injury (ALT or AST > 3 x ULN and TBIL \geq 2 x ULN and ALP < 2 x ULN), eDISH plot may be provided as well

The following listings will be produced for the laboratory data:

- Listing of all laboratory data with values flagged to show the corresponding CTC grades the classifications relative to the laboratory reference ranges
- Listing of notable laboratory abnormalities (i.e. CTC grade 3 or 4 laboratory toxicities).

2.8.4 Other safety data

2.8.4.1 ECG and cardiac imaging data

ECG data will be presented as follows:

- Number and percentage of patients with clinically notable ECG values will be summarized.
- ECG evaluations for all patients with at least one abnormality will be listed.

The notable criteria for PR are

- > 200 ms post-baseline and \leq 200 ms at baseline
- Increase > 25% compared to baseline to a post-baseline value > 200 ms

The notable criteria for QRS are

- > 110 ms post-baseline and \leq 110 ms at baseline
- Increase > 25% compared to baseline to a post-baseline value > 110 ms

The notable criteria for QT and QTcF are

- > 450 ms at any post-baseline and \leq 450 ms at baseline
- > 480 ms at any post-baseline and \leq 480 ms at baseline
- > 500 ms at any post-baseline and \leq 500 ms at baseline
- an increase from baseline > 30 ms at any post-baseline
- an increase from baseline > 60 ms at any post-baseline

For 24hr Holter assessment, all findings will be listed and notable finding will be summarized based on clinical review of the Holter ECG data using the following criteria

- Potentially related to QT (Ventricular extra beats $\geq 200/24h$, Ventricular tachycardia, Non-sustained VT, Sustained VT, Ventricular fibrillation, Ventricular flutter, Syncope, Torsades de Pointes, Bradycardia $< 40/min$)
- Potentially related to conduction (New Left Bundle Branch Block, New Right Bundle Branch Block, Mobitz II AV block, Complete heart block Grade III)
- Other relevant arrhythmias (Atrial fibrillation, Atrial flutter)

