2.2.6 ECG Monitoring

Cardiac monitoring will include 12-lead Safety ECGs at pre-dose (Day 1) and 1.5 hours post-dose at each visit the patient receives study drug. The Safety ECGs are the primary cardiac safety assessment, and their rationale is to assess the maximum change in QTcF in each individual patient each time they receive study drug at the site. The 12-lead safety ECGs are read in real-time on-site by the PI or other qualified physician (e.g., cardiologist), and if there is QT prolongation (QTcF > 480 ms or increase > 60 ms from baseline assessment), patients are to be managed according to the QT Monitoring Flow Chart in [Figure 7-2](#).

In addition, 24-hour continuous 12-lead Holter recordings will be performed at baseline, Weeks 2, 12, 14, 36, and as applicable at Week 72 and at the end of treatment visit in the optional Extension phase. The 24 hour Holter assessments are not intended to provide real-time assessment of cardiac intervals and cardiac rhythm; the recordings are read centrally.

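### Final SAP 2.8.4.1: apart from bundle branch block, the Holter criteria set no baseline condition, so a pre-treatment arrhythmia seen again later can be counted in the osilodrostat-only summary

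*SAP*

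**What the plan says.** Final SAP 2.8.4.1 deals with 12-lead intervals and Holter findings in turn.

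The 12-lead criteria all refer to baseline. Each absolute QT/QTcF limit has the form "> 480 ms at any post-baseline and \leq 480 ms at baseline". PR and QRS each have one criterion of that form and a second that flags a rise of more than 25% to a value above the limit. QT and QTcF also have rises of more than 30 and more than 60 ms.

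For the Holter, all findings are listed and "notable finding will be summarized based on clinical review of the Holter ECG data using the following criteria". The criteria form three groups:
- The first opens with "Potentially related to QT (Ventricular extra beats $\geq 200/24h$, Ventricular tachycardia, Non-sustained VT, Sustained VT" and goes on to other ventricular arrhythmias, syncope and bradycardia below 40 per minute.
- The conduction group is "New Left Bundle Branch Block, New Right Bundle Branch Block, Mobitz II AV block, Complete heart block Grade III".
- The last group is "Other relevant arrhythmias (Atrial fibrillation, Atrial flutter".

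Only the two bundle branch blocks are qualified as new.

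The baseline recording exists. Protocol 2.2.6 states that "24-hour continuous 12-lead Holter recordings will be performed at baseline, Weeks 2, 12, 14, 36", with Week 72 and the end-of-treatment extension visit added as applicable. Protocol Table 7-6 places the baseline Holter at Day -14 to -1, read centrally.

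Final SAP 2.8 limits safety in the final report to osilodrostat exposure. Placebo-arm data from the placebo-controlled period are excluded.

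**The concern.** A criterion without a baseline condition measures prevalence on treatment. A summary of notable findings on osilodrostat will be read as what appeared on osilodrostat, and with no placebo column the patient's own baseline is the only control left. The first Holter group is labelled as possibly QT-related, and QT prolongation and arrhythmogenic potential are areas of special interest in Protocol 8.1.3, so readers will look at this table.

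Because the list marks two items as new, the same condition is hard to read into the items that lack the word. What is at stake is the interpretation of one descriptive safety summary.

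**Working it through.** The plan states no Holter count or rate, so there is no figure to reproduce. The check is a comparison of definitions, followed by an illustration of scale.

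**1. How similar outputs treat baseline**

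| Output (Final SAP) | Baseline condition on the limit | Patient already abnormal at baseline |
|---|---|---|
| PR, QRS (2.8.4.1) | yes, first criterion | flagged if the rise exceeds 25% |
| QT/QTcF (2.8.4.1) | yes, absolute limits | flagged if the rise exceeds 30 or 60 ms |
| Blood pressure, pulse (2.8.4.2) | limit paired with a change from baseline | counted only with that change |
| Graded laboratory tests (2.8.3) | none, and the plan says so | baseline-to-worst shift table |
| Holter, bundle branch block | must be new | not counted |
| Holter, all other items | none | no rule, no shift table |

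**2. Does another section fill the gap?** The definition of treatment-emergent in Final SAP 2.8.1 covers adverse events only. The core SAP (1 April 2019), section 2.8.4.1, has an ECG shift table but no Holter criteria, and the final SAP's ECG section has no shift table. Neither document supplies a baseline rule for Holter findings.

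**3. The criterion applied literally to hypothetical patients**

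| Baseline Holter | Week 36 Holter | Criterion met? | What happened |
|---|---|---|---|
| 600 extra beats | 250 | yes, 250 ≥ 200 | ectopy fell |
| below 200 | 250 | yes | new |
| 250 | 5,000 | yes | 5,000 / 250 = 20-fold rise |
| atrial fibrillation | atrial fibrillation | yes | unchanged |

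Four different courses meet the criterion in the same way.

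**4. Which arrhythmias can be pre-existing?** Exclusion criterion 6 (Protocol 5.3) removes patients with a history of sustained ventricular tachycardia, clinically significant bradycardia or advanced heart block. It does not name ventricular ectopy, asymptomatic bradycardia or atrial fibrillation/flutter. The issue mainly concerns those three.

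**5. Scale, on assumptions only.** Let N = 69 (planned enrolment) and let p be the assumed proportion meeting a criterion at baseline. Suppose that every such finding recurs on a later Holter, none is discounted at review, and the drug has no effect. Expected patients flagged = N × p; chance of at least one = 1 − (1 − p)^N.

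| Assumed p | 69 × p | Chance of at least one |
|---|---|---|
| 1% | 0.69 | 0.500 |
| 5% | 3.45 | 0.971 |
| 10% | 6.9 | 0.999 |

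Incomplete recurrence scales the count down: with p = 5% and half recurring, 69 × 0.05 × 0.5 = 1.7 patients.

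**6. Placebo-arm patients.** Final SAP 2.1.1 defines baseline as the last assessment on or before the first dose of study treatment, and study treatment includes placebo. An arrhythmia that arises on placebo and persists after the Week 12 switch would be absent at that baseline. A new-since-baseline rule alone would then count it as new on osilodrostat.

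**The case against.** The strongest reply is that the summary rests on clinical review. Where this SAP wants mechanical counting it says so: Final SAP 2.8.3 has laboratory grades assigned by program from observed values, without clinical assessment. A reviewer with the baseline recording could set aside a known finding, and the listing lets anyone recover baseline status by hand. This stands in part. It means that a pre-existing arrhythmia can be counted, not that it will be. But no rule tells the reviewer what to do, so the count depends on unstated judgement.

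A second reply is that requiring absence at baseline could hide harm. The patient going from 250 to 5,000 extra beats would drop out of the notable count. This is right. PR and QRS do not work that way either, since their second criterion keeps worsening visible. It shapes the fix.

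A third is that the Holter is secondary: Protocol 2.2.6 names the 12-lead safety ECG as the primary cardiac safety assessment. That limits the importance of the point but does not remove it.

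A reader might also infer that adverse events of special interest are over-counted. The documents do not support that. Those events come from routine adverse event collection (Protocol 8.1.3.3), and the rule of new or worsened from baseline applies to them (Final SAP 2.8.1).

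**Conclusion.** The point holds as a gap in definition. Apart from bundle branch block, the Holter criteria do not separate findings present before treatment from those that appear on it, and no shift table, emergent rule or placebo column in the final analysis makes up for this. In practice it concerns ventricular ectopy, asymptomatic bradycardia and atrial fibrillation/flutter.

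Three stronger readings are tempting and should not be drawn:
- *Every pre-existing arrhythmia is counted.* It must recur on a later Holter and survive clinical review.
- *The summary overstates emergent arrhythmia by a known multiple.* Such a multiple needs a baseline prevalence, an emergent rate and a recurrence rate, and the documents give none of them. The counts in the working show scale only.
- *The table cannot show improvement or worsening.* The SAP does not fix the layout, and a by-visit table with a baseline column would be compatible with the text. The defect is that nothing requires one.

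The primary and key secondary analyses are unaffected. This is a cheap improvement to a descriptive safety table.

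**What to change.** In Final SAP 2.8.4.1, summarize each Holter criterion in two rows:
- (a) new: met after baseline and not met on the baseline Holter;
- (b) present at baseline.

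For ventricular extra beats, add a baseline-to-worst shift or a stated worsening rule, in parallel with the PR and QRS criterion for a rise above 25%, so that a patient who worsens from an abnormal baseline stays visible.

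State which Holter is the reference for placebo-arm patients who switch at Week 12. The choice needs care. Protocol Table 7-6 starts the 24-hour Week 12 recording before the dose, and Protocol 4.1 starts open-label drug immediately after that visit, so the recording may span the switch.

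The cost is a few sentences in the SAP and a small amount of extra tabulation. The baseline Holter is already scheduled and centrally read, so no new data are needed.

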2.8.4.2 Vital signs

All vital signs data (height (cm), weight (kg), body temperature ($^{\circ}C$), supine pulse rate (beats per minute), and supine systolic/diastolic blood pressure (mmHg)) will be listed by patient and visit/time, and abnormalities will be flagged on listing. For blood pressure, two measurements are planned to be taken and the average will be used for analysis purpose. Shift table based on notable value will be provided for vital signs. Change over time from baseline will be summarized.

The criteria for clinically notable abnormalities are defined as follows:

Clinically notable elevated values

- Systolic BP: ≥ 180 mmHg and an increase ≥ 20 mmHg from baseline
- Diastolic BP: ≥ 105 mmHg and an increase ≥ 15 mmHg from baseline.
- Supine pulse: ≥ 120 bpm with increase from baseline ≥ 15 bpm
- Weight: Increase from baseline of $\geq 10\%$

Clinically notable below normal values

- Systolic BP: ≤ 90 mmHg and a decrease ≥ 20 mmHg from baseline
- Diastolic BP: ≤ 50 mmHg and a decrease ≥ 15 mmHg from baseline
- Supine pulse: ≤ 50 bpm with decrease from baseline ≥ 15 bpm
- Weight: Decrease from baseline of $\geq 5\%$

Vital signs (supine BP, HR & temperature) reporting of results will include

- shift table baseline to worst on-treatment result
- table with descriptive statistics at baseline, one or several post-baseline time points and change from baseline to this/these post-baseline time points.

2.8.4.3 Tumor volume and longest dimension

For tumor volume evaluated by MRI (or CT) by central assessment of an independent neuroradiologist, descriptive summary of actual tumor volumes as well as its change from baseline will be provided at visits where evaluation is scheduled (Week 26, 48, 72, and 96). The independent neuroradiologist measured the tumor volume, when it cannot be easily distinguished, the whole pituitary gland was measured. For the analysis, only measurements of the tumor volume are used.

Patients with pituitary volume assessments at baseline will be monitored and measured at the pre-specified timepoints. Patients with no visible or measurable pituitary tumour at baseline will be assessed at all timepoints whether a tumour becomes visible and it can be measured accordingly. Patients will be assessed whether the pituitary tumour is within or goes beyond the sella turcica at each time points of MRI assessment. Measurements and available information about new lesions of patients with only pituitary gland dimensions at baseline will be listed.

[figure not shown]
2.8.4.4 Columbia Suicide Severity Reporting Scale (C-SSRS)

C-SSRS data will be mapped to Columbia Classification Algorithm for Suicide Assessment (C-CASA) as per FDA guidance on suicidality (Food and Drug Administration 2010). The proportion of patients who have committed suicide, attempted suicide, done preparatory actions toward imminent suicidal behavior, suicidal ideation, and self-injurious behavior without suicidal intent will be summarized by treatment arm.

2.9 Patient-reported outcomes

The CushingQoL score is identified as the primary PRO variable of interest. EQ-5D utility index and visual analogue scale (VAS) scores, and Beck Depression Inventory-II (BDI) total score are identified as secondary PRO variables of interest (see [Section 5.4](#) for the score derivations). The FAS will be used for analyzing PRO data. No multiplicity adjustment will be applied.

Descriptive statistics will be used to summarize the actual and change from baseline for the scores at each scheduled assessment including critical time points such as from baseline to Week 12 and Week 48, from Week 12 to Week 36 and from Week 36 to Week 48 etc.

3 Sample size calculation

Eligible patients will be stratified at randomization according to history of pituitary irradiation (yes/no). Based on the LCI699C2201 study, it is assumed that approximately 20% of randomized patients will have a history of pituitary radiation.

With 2:1 randomization ratio, to detect a difference of 45% in complete response rate between 60% in osilodrostat arm and 15% in placebo arm (equivalent odds ratio equals 8.5), a sample size of 42 patients in osilodrostat arm and 21 patients in placebo arm will provide 91% power based on a 1-sided CMH exact test at the 0.025 level. In order to adjust for drop-outs, an additional 10% patients will be enrolled. Thus a total of approximately 69 patients will be enrolled in the study.

The analysis of the key secondary objective will be based on the 2-sided 95% confidence interval constructed using the Clopper-Pearson exact method. If the lower bound of this 95% confidence interval is $\geq 30\%$, the null hypothesis will be rejected and the complete response rate will be considered at least 30% at Week 36. Both the SOM230G2304 trial of Pasireotide LAR and the SOM230B2305 trial of Pasireotide s.c. were powered to show a response rate where the lower bound of the 95% confidence interval was $\geq 15\%$. Therefore an increase in this lower bound of the 95% confidence interval to a threshold of $\geq 30\%$ would provide a significant improvement in clinical benefit to this patient arm.

The above testing on the key secondary objective will only be carried out if the null hypothesis for the primary objective is rejected. This sequential procedure will ensure preservation of the overall 2-sided type 1 error at 5%.

Assuming a 60% complete response rate at Week 36, and less than 50% discontinuation rate of patients in placebo arm prior to Week 12. For the 69 patients in the pooled population, there is higher than 98% chance that the lower bound of 2-side 95% exact CI (based on Clopper-Pearson method) of the observed response rate is larger than 30%.

4 Change to protocol specified analyses

In the SAP for the core CSR, clarification is made that efficacy was summarized by randomized treatment arms during the placebo-control period and by randomized treatment arms and for overall patients during the open-label period. Safety was summarized by randomized treatment arms during the placebo-control period.

For the overall study period, only safety data associated with osilodrostat treatment was summarized, which means safety data in placebo-arm collected during placebo-control period was excluded from the analysis. The same approach will be followed for the final CSR.

5 Appendix

5.1 Imputation rules

Partial dates will remain partial in the data listings. For the purpose of analysis, the following imputation rules will be used to impute the partial dates.

5.1.1 Study drug

Any partial dates or gaps between dates should be resolved for analysis purpose. The end date of study drug is derived by using the last non-zero dose end date from the dose administration record CRF page. If after DBL the partial dates still exist for end date, the imputation rule is as below:

If month and year is present, but day is missing, set the end date to be the first day of the month. If after imputation of day, study medication end date is earlier than study medication start date set study medication end date to study medication start date.

5.1.2 AE date imputation

Summary tables for adverse events (AEs) have to include only AEs that started or worsened during the on-treatment period, the treatment-emergent AEs. However, all safety data (including those from the post-treatment period) will be listed and those collected during the pre-treatment and after 30 days of post-treatment period or safety follow-up whichever is later are to be flagged.

Any missing onset date, causality, or severity must be queried for resolution. Unsolved missing values will be imputed according to the following:

AE end date imputation:

1. If the AE end date month is missing, the imputed end date should be set to the earliest of the (treatment follow up period date, 31DECYYYY, date of death).
2. If the AE end date day is missing, the imputed end date should be set to the earliest of the (treatment follow up period date, last day of the month, date of death).
3. If AE year is missing or AE is ongoing, the end date will not be imputed.

AE start date imputation:

1. If the AE start date year value is missing, the date uncertainty is too high to impute a rational date. Therefore, if the AE year value is missing, the imputed AE start date is set to NULL.
2. If the AE start date year value is less than the treatment start date year value, the AE started before treatment. Therefore:
 - a. If AE month is missing, the imputed AE start date is set to the mid-year point (01JulYYYY).
 - b. Else if AE month is not missing, the imputed AE start date is set to the mid-month point (15MONYYYY).
3. If the AE start date year value is greater than the treatment start date year value, the AE started after treatment. Therefore:
 - a. If the AE month is missing, the imputed AE start date is set to the year start point (01JanYYYY).
 - b. Else if the AE month is not missing, the imputed AE start date is set to the later of (month start point (01MONYYYY), AE start reference date + 1 day).

4. If the AE start date year value is equal to the treatment start date year value:
 - a. And the AE month is missing the imputed AE start date is set to the AE reference start date + 1 day.
 - b. Else if the AE month is less than the treatment start month, the imputed AE start date is set to the mid-month point (15MONYYYY).
 - c. Else if the AE month is equal to the treatment start date month or greater than the treatment start date month, the imputed AE start date is set to the later of (month start point (01MONYYYY), AE start reference date + 1 day).

If complete (imputed) AE end date is available and the imputed AE start date is greater than the (imputed) AE end date, then imputed AE start date should be set to the (imputed) AE end date.

5.1.3 Concomitant medication date imputation

The start/stop dates recorded in the electronic case report form (eCRF) will be used to identify when a concomitant medication or a significant non-drug therapy was taken during the study. Concomitant medications and significant non-drug therapies after the start of the study treatment will be listed and summarized by ATC class and standardized medication term for the Safety Set. These summaries will include medications starting on or after the start of study treatment or medications starting prior to the start of study treatment and continuing after the start of study treatment. Any prior medications and significant non-drug therapies starting and ending prior to the start of study treatment will be listed. These analyses will be based on Safety Set.

Any missing date will be queried for resolution. For any unsolved missing dates, the following rules in the following order will be applied to decide if a concomitant medication or a significant non-drug therapy was taken after the start of the study treatment and to decide if the data should be included in the summary table. Originally collected date will be listed in listings.

CM end date imputation:

1. If CM end day is missing and CM month/year are non-missing then impute CM day as the minimum of treatment end date and the last day of the month.
 2. If CM end day/month are missing and CM year is non-missing then impute CM day as the minimum of treatment end date and the end of the year (31DECYYYY).
 3. If CM day/month/year is missing then use the treatment end date + 1 day as the imputed CM end date.
 4. If imputed CM end date is less than the CM start date, use the CM start date as the imputed CM end date.
1. CM start date imputation: If the CM start date year value is missing, the imputed CM start date is set to one day prior to treatment start date.
 2. If the CM start date year value is less than the treatment start date year value, the CM started before treatment. Therefore:
 - a. If the CM month is missing, the imputed CM start date is set to the mid-year point (01JulYYYY).

- b. Else if the CM month is not missing, the imputed CM start date is set to the mid-month point (15MONYYYY).
3. If the CM start date year value is greater than the treatment start date year value, the CM started after treatment. Therefore:
 - a. If the CM month is missing, the imputed CM start date is set to the year start point (01JanYYYY).
 - b. Else if the CM month is not missing, the imputed CM start date is set to the month start point (01MONYYYY).
4. If the CM start date year value is equal to the treatment start date year value:
 - a. And the CM month is missing or the CM month is equal to the treatment start date month, then the imputed CM start date is set to one day prior treatment start date.
 - b. Else if the CM month is less than the treatment start date month, the imputed CM start date is set to the mid-month point (15MONYYYY).
 - c. Else if the CM month is greater than the treatment start date month, the imputed CM start date is set to the month start point (01MONYYYY).

If complete (imputed) CM end date is available and the imputed CM start date is greater than the (imputed) CM end date, then imputed CM start date should be set to the (imputed) CM end date.

